8.6.2 Analysis of primary efficacy endpoint

The primary efficacy endpoint defined in section 4.1.1 will be analysed using the PP set as outlined below:

For the primary endpoint, VE will be evaluated as 1 minus the relative risk (RR) of vaccinated (30 µg/strain VLP vaccine) and unvaccinated (placebo) subjects to become infected with protocol-defined respiratory illness caused by one or more vaccine-matched strains in a timeframe of 14 or more days following vaccination (i.e. the proportion of subjects with one or more episodes of respiratory illness shown to be caused by viral types/subtypes that are matched and/or antigenically similar to the strains covered in the vaccine formulation).

VE will be calculated using the following formula:

$$\text{VE} = (1 - \text{RR}) = (1 - \text{ARV}/\text{ARU}) * 100 \%$$

Where:

RR = relative risk

ARV = attack rate in vaccinated subjects; and

ARU = attack rate in unvaccinated subjects.

The VE success criterion is defined as a $> 40\%$ lower limit of the two-sided 95 % CI.

The analyses of the primary efficacy endpoint will be repeated for the FAS.

The primary endpoint will be summarized descriptively with VE and its 95% CI. Sub-analyses (VE and its 95% CI) by each strain (homologous A/Michigan/45/2015 [H1N1], homologous A/Hong Kong/4801/2014 [H3N2], homologous B/Brisbane/60/2008 and homologous B/Phuket/3073/2013) and by age group (18-49 and 50-64) will be summarized.

8.6.2.1 Multiplicity

Multiplicity adjustment will not be done for the primary endpoint because there is only one.

8.6.2.2 Methodology for computing CI

8.6.2.2.1 Exact 95% CIs

The 95% CI around RR will be calculated based on score confidence limits.

SAS® Code:^{Reference (4,5)}

```
Proc freq data= ADZ (with the appropriate analysis dataset) ;
table group*resp/relrisk (cl=SCORE) ;
run ;
```

Note: LB=1-95% Upper Confidence Limit

8.6.3 Analysis of secondary efficacy endpoints

The secondary efficacy endpoints which are defined in 4.1.2 will be analysed in the following manner:

VE and 95% CI will be calculated for the secondary efficacy endpoints using the same formula indicated for the primary efficacy analysis. For secondary efficacy endpoints, the sub-analyses (VE and its 95% CI) by each strain (where applicable) and age group will be summarized.

An overall summary of subjects with ILI and summaries of subjects of each ILI symptom will be presented by treatment group.

All the secondary efficacy analyses will be based on the PP and will be repeated for the FAS as well.

8.6.3.1 Multiplicity

Multiplicity adjustment will not be done for the secondary efficacy endpoints.

8.6.3.2 Methodology for computing CI

8.6.3.2.1 Exact 95% CIs

The 95% CIs will be calculated in the same way as for the primary analysis mentioned above (Section 8.6.2).

8.6.4 Analysis of exploratory endpoint(s)

The exploratory efficacy endpoints which are defined in Section 4.1.3 will be analysed using the same formula indicated for the primary efficacy analysis. The sub-analyses (VE and its 95% CI) by age group and by strain (where applicable) will be summarized.

And overall summaries of subjects with respiratory illness symptoms and subjects with systemic symptoms , and sumaries of subjects with each respiratory illness and systemic symptom will be presented by treatment group and age group.

In addition, an individual listing will be included to present details of the results of RT-PCR and typing (laboratory-confirmed influenza vaccine matched, mismatched strains, or un-typed strains, respiratory illness symptoms, and ILI by subject and age stratum.

All the exploratory efficacy analyses will be based on the PP and will be repeated for the FAS as well.

8.7 Analysis of immunogenicity

8.7.1 Immunogenicity Evaluations

Immunogenicity will be evaluated by the humoral immune response (HI, MN, and SRH assays) and the CMI response induced in subjects on Days 0 and 21 in a subset of 400 subjects (300 from the VLP vaccine group and 100 from the placebo group) from selected sites. The North American sites selected for this subset of 400 subjects will be pre-defined prior to study start and will target providing a representative age distribution. The subjects identified for the immunogenicity analyses will also be stratified by age group (1:1 ratio).

For the immunogenicity analysis of the HI assays against the homologous strains, the point estimates and the corresponding two-sided 95% CI will be calculated to determine if the CBER criteria for licensure for influenza vaccine are met. The following analyses for the HI assay (homologous strains) will be performed on the IPP:

8.7.2 Analysis of Secondary Endpoints

The secondary immunogenicity endpoints are defined in section 4.3.1.

HI antibody titers will be analyzed and evaluated according to the CBER criteria, using a stepwise closed testing procedure as follows:

- GMTs of HI antibody: The point estimates and the corresponding two sided 95% CI by treatment group and strain will be calculated as the antilog of the mean and 95% CI of log transformed titer values on Days 0 and 21;
- SC rate: The point estimates and the corresponding two-sided 95% CI for subjects achieving SC by treatment group and strain will be calculated to determine whether the lower bound of the CI will meet or exceed 40%;
- SP rate: The point estimates and the corresponding two-sided 95% CI for subjects achieving SP by treatment group and strain will be calculated to determine whether the lower bound of the CI will meet or exceed 70%.
- GMFR: the geometric mean of the ratio of GMTs (Day 21/Day 0).

For SC and SP rates, the following stepwise closed testing procedure will be applied while evaluating the results against the CBER criteria (for SC rate, the lower bound of the 95% CI will meet or exceed 40%; for SP rate, the lower bound of the 95% CI will meet or

exceed 70%). The stepwise closed testing procedure will be continued until the first rejection of the CBER criteria occurs.

Step (1) A/H1N1:SC rate → SP rate → Step (2) A/H3H2:SC rate → SP rate → Step (3) B/Brisbane:SC rate → SP rate → Step (4) B/Phuket:SC rate → SP rate

MN antibody response against the homologous influenza strains on Days 0 and 21 will be analysed as follows:

- GMTs of MN antibody on Days 0 and 21 (as defined above for HI);
- SC rate: the proportion of subjects in a given treatment group with either a ≥ 4 -fold increase in reciprocal MN titers between Day 0 and Day 21 or a rise of undetectable MN titer (i.e. < 14.1) pre-vaccination (Day 0) to an MN titer of ≥ 56.4 at Day 21 post-vaccination. GMFR: the geometric mean of the ratio of GMTs (Day 21/Day 0).

SRH antibody response against the homologous influenza strains will be analysed as follows:

- GMAs of SRH antibody on Days 0 and 21;
- SC rate: proportion of subjects in a given treatment group showing at least 50% increase in GMA between Days 0 and 21;
- SP rate: the proportion of subjects in a given treatment group attaining an area ≥ 25 mm² following vaccination (Day 21);
- GMFR: the geometric mean of the ratio of GMAs (Day 21/Day 0).

The GMFR will be derived by using ANCOVA to model the difference in the log of the titer values between Day 21 and Day 0, with treatment group as main effect and baseline titer as covariate.

The GMTs, GMFRs, SP and SC rates of the HI and MN antibody assay and the GMAs, GMFRs, SC rates, and SP rates for the SRH antibody assay will be compared between the treatment groups using descriptive statistics and 95% CI. For SC rate and SP rate, Fisher's exact tests will be used. GMT for HI, MN and GMA for SRH will be compared between treatment groups using analysis of variance (ANOVA) model. GMFR for HI, MN and SRH will be compared using analysis of covariance (ANCOVA) model.

A sub-analyses stratified by age group for the secondary immunogenicity endpoints will be performed. The analyses of the secondary immunogenicity endpoints will be repeated for the FAS.

An individual listing will be provided to include all assay results (HI, MN and SRH) and whether a particular subject has seroconverted/seroprotected based on IPP set.

In addition, the below listed figures will be generated:

- Reverse Cumulative Distribution Curves (RCDC) for Homologous Strains Measured and Heterologous Strains Measured by HI based on IPP.
- RCDC for Homologous Strains Measured by HI based on FAS.
- RCDC for Homologous Strains Measured by MN based on IPP.
- RCDC for Homologous Strains Measured by SRH based on IPP.

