4.3 Immunogenicity endpoints (subset of subjects)

4.3.1 Secondary endpoints

- HI antibody response induced by the Quadrivalent VLP Influenza Vaccine against the homologous and heterologous influenza strains on Days 0 and 21 in a subset of 400 subjects (300 who received the VLP vaccine and 100 who received the placebo). HI antibody titers will be analyzed as follows:
 - Geometric Mean Titers (GMT) of HI antibody on Days 0 and 21;
 - Seroconversion (SC) rate: the proportion of subjects in a given treatment group with either a ≥ 4 -fold increase in reciprocal HI titers between Day 0 and Day 21 or a rise of undetectable HI titer (i.e. < 10) pre-vaccination (Day 0) to an HI titer of ≥ 40 on Day 21;
 - Seroprotection (SP) rate: the proportion of subjects in a given treatment group attaining a reciprocal HI titer of ≥ 40 on Day 21 (the percentage of vaccine recipients with a serum HI titer of at least 1:40 following vaccination);
 - Geometric Mean Fold Rise (GMFR): the geometric mean of the ratio of GMTs (Day 21/Day 0).
- MN antibody response induced by the Quadrivalent VLP Influenza Vaccine against the homologous influenza strains on Days 0 and 21, in the subset of 400 subjects, will be analysed as follows:
 - GMTs of MN antibody on Days 0 and 21;
 - SC rate: the proportion of subjects in a given treatment group with either a ≥ 4 -fold increase in reciprocal MN titers between Day 0 and Day 21 or a rise of undetectable MN titer (i.e. < 14.1) pre-vaccination (Day 0) to an MN titer of ≥ 56.4 at Day 21 post-vaccination ;GMFR (Day 21/Day 0).

Note: A number of studies show the MN assay to have a two-fold or higher sensitivity than the HI assay. However, there is still limited data available on the comparative

sensitivities of these two assays and the data that is available and is largely focused on H1N1 and H3N2. As a result, since this is a secondary analysis with a relatively small sample size, a conservative approach was taken by using the HI assay correlates of protection for the MN assay.

- SRH antibody response induced by the Quadrivalent VLP Influenza Vaccine against the homologous strains on Days 0 and 21 in a subset of 400 subjects will be analysed as follows:
 - Geometric Mean Areas (GMA) of SRH antibody on Days 0 and 21;
 - SC rate: proportion of subjects in a given treatment group showing at least 50 % increase in GMA between Days 0 and 21;

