8.7.2.2 Methodology for computing CI

8.7.2.2.1 95% CIs

The 95% CI for GMTs will be obtained within each group separately. The 95% CI for the mean of log-transformed titer/concentration will be first obtained assuming that log-transformed concentrations/titers are normally distributed with an unknown variance. The 95% CI for GMTs will be then obtained by exponential-transformation (anti-log with power 10) of the 95% CI for the mean of log-transformed titers.

SAS® Code for comparing GMTs:

```
PROC MIXED DATA=<Data>; * specify and sub-select data set as applicable;
  *BY Agegrp; * as applicable;
  CLASS trtpn; * other factors may be added, if applicable;
  MODEL AVAL = trtpn; * AVAL=logtiter
    * add factors and options (e.g. ALPHA=.. Solutions) as applicable;
    LSMEANS trtpn / CL ALPHA=0.05 STDERR; * modify/adapt as applicable
  Ods output LSMEANS = _outmix;
  RUN;
  QUIT;
Data _outmix;
Set _outmix;
GMT= 10** (Estimate);
GMT_LCL = 10** (Lower);
GMT_UCL = 10** (Upper);
RUN;
```

SAS® Code for comparing GMFR:

```
PROC MIXED DATA=<Data> (analysis dataset) ;
  class trtpn;
  model diff= trtpn Base; * diff = log10Day21 - log10Day0. Base=log10Day0
  Lsmeans trtpn/cl alpha=0.05;
  Ods output LSMEANS =_outmix;
  run;
  Quit;
  Data _outmix;
  Set _outmix;
  GMFR = 10** (Estimate) ;
  GMFR_LCL = 10** (Lower) ;
  GMFR_UCL = 10** (Upper) ;
  Run;
```

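### The Day 21 GMT/GMA comparison between arms omits the Day 0 titre that the neighbouring GMFR model already uses, so the SAP gives two answers to one question and does not say which leads

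*SAP*

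**What the plan says.** The SAP lists GMTs (GMAs for SRH) on Days 0 and 21 as secondary immunogenicity endpoints; for HI the entry reads "Geometric Mean Titers (GMT) of HI antibody on Days 0 and 21". The subset has 400 subjects, "300 from the VLP vaccine group and 100 from the placebo group", and Protocol Table 5 plans a blood sample from each on both days.

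Two between-arm models follow in SAP 8.7.2.

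- **Titre level.** "GMT for HI, MN and GMA for SRH will be compared between treatment groups using analysis of variance (ANOVA) model". The code in 8.7.2.2 is "MODEL AVAL = trtpn; * AVAL=logtiter". A code comment leaves room for more terms, "CLASS trtpn; * other factors may be added, if applicable", but names none and does not mention baseline.
- **Fold rise.** "GMFR for HI, MN and SRH will be compared using analysis of covariance (ANCOVA) model", specified "with treatment group as main effect and baseline titer as covariate". The code is "model diff= trtpn Base; * diff = log10Day21 - log10Day0. Base=log10Day0".

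SAP 8.7.2 also calls for age-group sub-analyses and a repeat in the FAS. Protocol 12.6.1 asks only for suitable ANOVA models for the MN and SRH comparisons.

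**The concern.** Log titres before and after vaccination in the same person are usually correlated. A Day 21 comparison that leaves out the Day 0 value then has a larger residual variance than it needs, and any chance difference between the arms at Day 0 passes into the estimate in proportion to the baseline slope. With only 100 placebo subjects, and about 50 per age stratum, such differences are not negligible.

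The covariate is planned for collection and is already derived in the next block of code. The SAP thus adjusts one of two closely related comparisons and not the other. For each assay and strain the reader would see a level comparison and a fold-rise comparison that may disagree. Nothing tells the reader that the two address the same question, or which to rely on. What is at stake is the clarity and precision of secondary comparisons, mainly where the difference between arms is small.

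**Working it through.** **1. The plan's own figure.** The only power stated for the subset (SAP section 5) is 80% overall from 97.4% per test. Four strains with SC and SP rates make 8 tests: 0.974^8 = 0.810, which agrees with 80%. The figure concerns SC and SP rates and does not depend on the GMT model. The documents give no power, SD or correlation for GMT, so everything numerical below rests on stated assumptions.

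**2. The two models give one contrast.** Write Y0 and Y21 for the log10 titres. The GMFR model is

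Y21 − Y0 = a + b·trt + c·Y0.

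Moving Y0 to the right gives

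Y21 = a + b·trt + (c + 1)·Y0.

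The treatment coefficient b and its standard error are unchanged. In 3,000 simulated data sets at each of three correlations, the largest difference between the two fits was about 1e-14, which is rounding error. The between-arm GMFR ratio, 10^b, is therefore the baseline-adjusted Day 21 GMT ratio.

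**3. Precision.** With the same correlation ρ in both arms, adjustment multiplies the variance of the contrast by 1 − ρ² and the interval width on the log scale by √(1 − ρ²).

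| ρ (assumed) | variance ratio | width ratio |
|---|---|---|
| 0.4 | 0.84 | 0.92 |
| 0.5 | 0.75 | 0.87 |
| 0.7 | 0.51 | 0.71 |

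Simulation at 300:100, with the slope estimated, gives width ratios of about 0.92 at ρ = 0.4 and 0.72 at ρ = 0.7. The narrowing is therefore about 8% to 28%.

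On the ratio scale, with an assumed SD of 0.6 log10, SE = 0.6·√(1/300 + 1/100) = 0.069. The unadjusted 95% limits lie a factor 10^(1.96·0.069) = 1.37 either side of the estimate. With adjustment the factor is 1.31 at ρ = 0.5 and 1.25 at ρ = 0.7.

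**4. Chance imbalance.** With a Day 0 SD of 0.5 log10 (assumed), one standard error of the baseline gap is 0.5·√(1/300 + 1/100) = 0.058 log10. With a baseline slope of 0.4 to 0.7, a gap of that size moves the unadjusted GMT ratio by 10^(0.4·0.058) = 1.055 to 10^(0.7·0.058) = 1.10, that is 5.5% to 10%. Over repeated randomisations this averages to zero.

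**5. Where it shows.** At 300:100 the unadjusted model has 96% to over 99.9% power for a 2-fold ratio (SD 0.7 down to 0.4), so large responses are safe either way. For a 1.5-fold ratio at SD 0.6, power is 72% unadjusted and 84% adjusted at ρ = 0.5. For a true 1.3-fold ratio at SD 0.5 and equal correlations of 0.4 to 0.7, the two models fall on opposite sides of p = 0.05 in about 13% to 33% of simulated subsets. At 150:50, the size of one age stratum under the planned 1:1 split, the range is about 13% to 29%.

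**The case against.** The strongest reply is that the adjusted analysis is already there. The GMFR ANCOVA is pre-specified for HI, MN and SRH, is covered by the age-group sub-analysis, and gives exactly the contrast that a baseline-adjusted GMT model would give. This stands. A reader might infer from the GMT code that the plan throws away the Day 0 information; taken as a whole it does not.

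A second reply is that the SAP defines no GMT ratio. The GMT code requests per-arm least-squares means with confidence limits and no difference between them, and SAP 7.1.2 attaches pairwise least-squares differences to the ANCOVA only. This weakens the point without removing it: 8.7.2 still commits in words to comparing GMT and GMA between arms by ANOVA, and does not call that comparison descriptive.

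Third, nothing formal depends on it. The CBER criteria, the stepwise procedure and the stated power concern SC and SP rates. That also stands.

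Two further inferences should be resisted. One is that the unadjusted comparison is biased: the imbalance is random error, and the ANOVA interval covers it on average. The other is that adjustment is worth 2 to 4.5 times the subjects. That requires assumed placebo correlations of 0.90 to 0.95, which the documents do not supply. Even then the reported interval narrows by only 15% to 35%, equivalent to 1/0.85² = 1.4 to 1/0.65² = 2.4 times the subjects. With equal correlations of 0.4 to 0.7 the gain is 1/0.84 = 1.2 to 1/0.51 = 2.0 times.

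**Conclusion.** The point holds as a minor one. The planned Day 21 GMT/GMA comparison is the less precise of two pre-specified answers to the same between-arm question, and the SAP states neither that they address the same question nor which one leads. With equal within-arm correlations of 0.4 to 0.7, adjustment keeps about 0.85 to 0.5 of the variance. A larger gain would need a higher correlation in the placebo arm. The algebraic identity of the GMFR contrast and the adjusted Day 21 contrast needs no assumption; the sizes do, since the documents give neither SDs nor correlations. The effect is confined to the interpretation of secondary immunogenicity comparisons, chiefly small ratios and age strata. A reader should not take this as a threat to the licensure criteria, the vaccine efficacy result or the sizing of the subset.

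**What to change.** In SAP 8.7.2 and 8.7.2.2:

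- For the Day 21 between-arm comparison only, fit `MODEL AVAL = trtpn Base`, with Base the log10 Day 0 titre (log10 Day 0 area for SRH). The term has no use for Day 0 itself.
- Keep the unadjusted per-arm GMTs and GMAs with within-arm confidence intervals on Days 0 and 21, labelled descriptive.
- State that the adjusted Day 21 GMT/GMA ratio and the GMFR ratio are the same contrast, and report it once per assay and strain.

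The cost is one covariate that the SAP already derives, a separate model call so that the descriptive per-arm values are not replaced by adjusted means, and a sentence of text. No new data are needed. The one small loss is that IPP membership (SAP 6.4) requires a Day 21 sample but does not name a Day 0 sample, so a subject without a Day 0 value would drop out of this contrast, as already happens for GMFR. The change should be made before database lock.

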8.7.2.1 Multiplicity

A multiplicity adjustment was done at the time of sample size determination (N=300) as described below:

The lower bound (LB) of the 95% CI for the percentage of subjects achieving SC and SP for the four homologous antigens will be compared to CBER's criteria as co-primary endpoints where a stepwise closed testing approach will be applied for multiplicity of hypothesis tests. The stepwise closed testing procedure will be stopped as soon as the LB of 95% CI for SC or SP of one strain does not meet CBER's criteria.

8.7.2.2 Methodology for computing CI

8.7.2.2.1 95% CIs

The 95% CI for GMTs will be obtained within each group separately. The 95% CI for the mean of log-transformed titer/concentration will be first obtained assuming that log-transformed concentrations/titers are normally distributed with an unknown variance. The 95% CI for GMTs will be then obtained by exponential-transformation (anti-log with power 10) of the 95% CI for the mean of log-transformed titers.

SAS® Code for comparing GMTs:

```
PROC MIXED DATA=<Data>; * specify and sub-select data set as applicable;
  *BY Agegrp; * as applicable;
  CLASS trtpn; * other factors may be added, if applicable;
  MODEL AVAL = trtpn; * AVAL=logtiter
    * add factors and options (e.g. ALPHA=.. Solutions) as applicable;
    LSMEANS trtpn / CL ALPHA=0.05 STDERR; * modify/adapt as applicable
  Ods output LSMEANS = _outmix;
  RUN;
  QUIT;
Data _outmix;
Set _outmix;
GMT= 10** (Estimate);
GMT_LCL = 10** (Lower);
GMT_UCL = 10** (Upper);
RUN;
```

SAS® Code for comparing GMFR:

```
PROC MIXED DATA=<Data> (analysis dataset) ;
  class trtpn;
  model diff= trtpn Base; * diff = log10Day21 - log10Day0. Base=log10Day0
  Lsmeans trtpn/cl alpha=0.05;
  Ods output LSMEANS =_outmix;
  run;
  Quit;
  Data _outmix;
  Set _outmix;
  GMFR = 10** (Estimate) ;
  GMFR_LCL = 10** (Lower) ;
  GMFR_UCL = 10** (Upper) ;
  Run;
```

8.7.2.2.2 Exact 95% CIs

The exact 95% CIs (Clopper-Pearson method) will be used for proportion of SC and SP subjects within a group.

SAS® Code for SC and SP (Exact 95% CIs):

```
PROC FREQ data=<Data> ;
  BY ANTIGEN trtpn;
  TABLE SC/out=CNT binomial; *SC or SP
  EXACT binomial;
  ODS OUTPUT binomialprop=bin (where=(name1 in ('XL_BIN', 'XU_BIN')));
  run;
```

8.7.3 Analysis of Exploratory Endpoint

The exploratory immunogenicity endpoint is defined in 4.3.2

The CMI response induced by the Quadrivalent VLP Influenza Vaccine against homologous and heterologous strains on Day 21 (in the subset of 400 subjects) will be compared between the treatment groups using non-parametric (Wilcoxon) models for each strain and parameter by age group and overall.

For CMI response CD4+ cells results will be presented along with available subjects (n), in terms of mean, median, SD, min and max. For the p-value calculation between the treatment groups for individual parameters, Wilcoxon rank-sum test will be used for Day 21, whereas the p-value will be calculated using Wilcoxon signed rank test for the difference between Day 0 and Day 21 values.

In addition, an individual listing will be provided to include CMI CD4+ cells response for each parameter with % response CD4+cells by subject and age stratum. The responses of each parameter will be illustrated using plots such as box plots by treatment group with parameters as X-axis and percentage of CD4+ T cells (%) as Y-axis.

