### 12.6.2 Analysis of Exploratory Endpoint

The exploratory immunogenicity endpoint is defined in Section [10.4.2.2](#).

The CMI response will be compared between the treatment groups using appropriate non-parametric (Wilcoxon) models. Additional details will be provided in the SAP.

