2.3 Exploratory objective(s)

Efficacy:

- To evaluate per age stratum, the efficacy, relative to placebo, of a single dose of the Quadrivalent VLP Influenza Vaccine given at a dose of 30 µg/strain, against laboratory-confirmed influenza illness caused by vaccine-matched strains;
- To evaluate the efficacy, relative to placebo, of a single dose of the Quadrivalent VLP Influenza Vaccine given at a dose of 30 µg/strain against mismatched influenza strains;

- To evaluate the efficacy, relative to placebo, of a single dose of the Quadrivalent VLP Influenza Vaccine given at a dose of 30 µg/strain, as measured by the incidence of subjects presenting with symptoms of protocol-defined respiratory illness, regardless of laboratory results.

Immunogenicity:

- To assess the cell-mediated immune (CMI) response against homologous and heterologous strains on Days 0 and 21 in a subset of 400 subjects (same subset as the immunogenicity subset).

Safety:

- To evaluate respiratory illness outcome, occurrences of pneumonia, new onset or exacerbations of cardio-respiratory conditions, and health care utilization of subjects administered the Quadrivalent VLP Influenza Vaccine given at a dose of 30 µg/strain, relative to subjects administered the placebo.

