4.3.2 Exploratory endpoints

- CMI response induced by the Quadrivalent VLP Influenza Vaccine against homologous and heterologous strains on Day 21 (in the subset of 400 subjects).

CMI responses against homologous and heterologous strains will be evaluated by measuring the % response in CD4+ Cells for parameters as below:

1. IFN- γ + IL-2+ TNF- α +
2. IFN- γ - IL-2+ TNF- α +
3. IFN- γ + IL-2- TNF- α +
4. IFN- γ + IL-2+ TNF- α -
5. IFN- γ - IL-2- TNF- α +
6. IFN- γ - IL-2+ TNF- α -
7. IFN- γ + IL-2- TNF- α -
8. SUM of IFN- γ + (the sum of all IFN- γ + responses; i.e. 1+3+4+7, from the list above)
9. SUM of IL-2+ (the sum of all IL-2+ responses; i.e. 1+2+4+6, from the list above)
10. SUM of TNF- α + (the sum of all TNF- α + responses; i.e. 1+2+3+5, from the list above)
11. SUM of total responsive (CD4+ expressing one cytokine; i.e. sum of all elements from the list above).

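### The between-arm CMI test in SAP 8.7.3 uses Day 21 values only; adjusting it for Day 0 is a low-cost gain in precision, of a size the documents cannot fix

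*SAP*

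**What the plan says.** SAP 8.7.3 sets the CMI tests in one sentence. It opens by speaking of p-values between the arms and goes on: "Wilcoxon rank-sum test will be used for Day 21, whereas the p-value will be calculated using Wilcoxon signed rank test for the difference". The difference meant is the change from Day 0 to Day 21. The tests are run for each strain and parameter, by age group and overall. Protocol 12.6.2 is less specific: "The CMI response will be compared between the treatment groups using appropriate non-parametric (Wilcoxon) models", with details left to the SAP.

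The endpoint in SAP 4.3.2 is the "CMI response induced by the Quadrivalent VLP Influenza Vaccine against homologous and heterologous strains on Day 21". The objective in SAP 2.3 names both days: "To assess the cell-mediated immune (CMI) response against homologous and heterologous strains on Days 0 and 21 in a subset of 400 subjects". Protocol Table 5 plans a CMI blood sample on Day 0 and again on Day 21 for the whole subset, which SAP 8.7.1 splits into 300 vaccine and 100 placebo subjects.

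For the antibody assays in the same subset, the SAP code for the fold rise (GMFR) adjusts for baseline, "model diff= trtpn Base", while the code for the GMT comparison does not, "MODEL AVAL = trtpn; * AVAL=logtiter" (both in 8.7.2.2).

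**The concern.** A rank-sum test on Day 21 compares the arms but makes no use of Day 0. A signed rank test uses Day 0, but it works on pairs within subjects and asks whether a single group has changed. It contains no contrast with placebo. Between them, the two planned tests leave the arm comparison without the baseline value.

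If a subject's Day 21 response is correlated with his or her Day 0 response, some of the spread in Day 21 values is predictable and could be removed. Leaving it in costs power, and most so in the by-age comparisons, where the groups are smaller.

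The wording adds a risk of misreading. The sentence opens by speaking of p-values between groups, so the signed rank result could be taken for an arm comparison. With 300 subjects against 100, the vaccine arm would also reach a significant change more easily than placebo for the same true change. Significance in one arm and not in the other would prove nothing about the difference between them.

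**Working it through.** The plan gives no CMI power, SD, effect size or correlation, so it has no CMI figure to reproduce. The subset's one power statement (SAP Section 5) concerns HI seroconversion and seroprotection rates and has no bearing here.

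**Inputs.** Arms of 300 and 100 (SAP 8.7.1). Two-sided alpha 0.05 (SAP 8.1). Reference power of 80%, chosen here. Day 0 to Day 21 correlation ρ, assumed over a range. Equal variance on both days, assumed.

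**Variance of the arm difference, relative to Day 21 only (normal theory).** Baseline-adjusted: 1 − ρ². Simple change from Day 0: 2(1 − ρ).

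**Detectable difference with the planned test.** (1.960 + 0.842) × √(1/300 + 1/100) = 0.323 SD. Dividing by √(3/π) = 0.977, for the efficiency of the rank-sum test, gives 0.331 SD. With adjustment, multiply by √(1 − ρ²). Within one age group, if it splits 150:50, the planned test detects about 0.47 SD.

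| ρ (assumed) | 0 | 0.3 | 0.5 | 0.7 | 0.8 |
|---|---|---|---|---|---|
| Variance ratio, adjusted | 1.00 | 0.91 | 0.75 | 0.51 | 0.36 |
| Variance ratio, change score | 2.00 | 1.40 | 1.00 | 0.60 | 0.40 |
| Detectable difference, adjusted (SD) | 0.331 | 0.316 | 0.287 | 0.236 | 0.199 |
| Normal-theory power, adjusted, where unadjusted has 80% | 80.0% | 83.6% | 89.9% | 97.5% | 99.7% |

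**Simulation of the rank tests.** The variance formulas are for normal data, so the rank tests were also simulated: 3,000 runs per setting, 300:100, skewed data with about 30% of Day 0 and placebo values at a floor, and a shift of 0.331 SD. Here ρ is the correlation on the underlying normal scale. The rank ANCOVA was the Quade form without age strata.

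| Power at ρ | 0 | 0.3 | 0.5 | 0.7 | 0.8 |
|---|---|---|---|---|---|
| Day 21 rank-sum (planned) | 78.3% | 77.6% | 79.7% | 78.4% | 77.6% |
| Rank ANCOVA | 78.5% | 81.3% | 87.4% | 95.7% | 98.8% |
| Rank-sum on change | 50.2% | 65.3% | 76.3% | 92.6% | 98.1% |

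With no true difference, the planned test rejected in 4.4% to 5.0% of runs and rank ANCOVA in 4.4% to 5.2%. Both hold their level. Rank ANCOVA lost no power at any ρ tried, whereas a rank-sum test on change was worse than the planned test up to ρ = 0.5.

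**Does the same point apply to the antibody titres?** Write Y0 and Y21 for log titres. The GMFR model is Y21 − Y0 = a + t × arm + b × Y0. Moving Y0 to the right gives Y21 = a + t × arm + (b + 1) × Y0. Only the baseline slope changes. The treatment effect t, its standard error and its p-value are the same on the same subjects. The GMFR model is therefore already the baseline-adjusted Day 21 comparison for HI, MN and SRH.

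**The case against.** The case for leaving 8.7.3 alone is fair. The protocol asks for Wilcoxon methods and the endpoint is the Day 21 response, so a rank-sum test on Day 21 is what was specified. CMI is exploratory, and no success criterion or power claim rests on it. The correlation is unknown, and at ρ = 0 adjustment gains nothing. Adjustment could also lose subjects: the immunogenicity per-protocol set (SAP 6.4) requires a Day 21 sample but does not name Day 0, and SAP 7.2 excludes missing values without replacing them. All of this stands and limits the weight of the point. It does not alter the fact that no CMI arm comparison uses a baseline sample that the plan collects for that assay.

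A reader might infer more than the documents support:

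- **That the planned test is biased or invalid.** It is not. A chance Day 0 difference between randomised arms is ordinary sampling variation, covered by the test's alpha.
- **That Day 0 is unused.** It enters the signed rank test; it is missing only from the arm comparison.
- **That the SAP rests the vaccine effect on the within-arm test.** It assigns the arm comparison to the rank-sum test. The sentence is loosely worded, and that calls for clarification only.
- **That the unadjusted GMT comparison has the same gap.** The equivalence shown above rules this out. The SAP also reports GMTs as group summaries on Day 0 as well as Day 21, and a Day 0 covariate makes no sense for the Day 0 value.

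**Conclusion.** The point holds as a minor matter of efficiency, limited to the CMI arm comparison. The planned rank-sum test is sound but forgoes a share of about ρ² of the available information: nothing at ρ = 0, 9% at 0.3, 25% at 0.5, 49% at 0.7 and 64% at 0.8. Those figures rest on normal theory, equal variances and a correlation that the documents do not give. The simulation shows the same pattern for rank tests under one assumed data shape. Because CMI is exploratory, no trial conclusion depends on the outcome. What justifies acting is the low cost: the sample is already planned, and the adjusted test lost no power in the settings tried.

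**What to change.** In SAP 8.7.3:

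1. Make the between-arm CMI test a rank ANCOVA (ranked Day 21 on ranked Day 0), stratified by age group for the overall comparison and run within each age group for the by-age results. It stays within the protocol's non-parametric approach. Do not substitute a rank-sum test on change.
2. Keep the Day 21 rank-sum test as supportive, including subjects with no Day 0 value, and say that these subjects drop out of the adjusted test.
3. State that the signed rank test is done within each arm and is not evidence of a difference from placebo.

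Leave the GMT and GMFR models as they are.

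The cost is a few lines of SAP text and a little new code, since the SAP gives no CMI code to extend. No new data are needed. The one downside is the possible loss of subjects without a Day 0 value from the adjusted test, which the supportive test makes visible.
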